11.4 Censoring Rules

Condition (within 14 days of surgery)	Censoring
No(t) Z ¹ but death report	Censoring at Study Day 14
No(t) Z ¹ and the subject is lost to follow-up or withdrew informed consent	Censoring at Study Day 14
No(t) Z ¹ within 14 days after surgery	Censoring at Study Day 14

¹Where Z is GI2, GI3, bowel movement, liquid oral diet, solid oral diet, discharge order written, actually discharged from hospital

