6.13. Gastrointestinal Function Assessment

Starting on Post-Operative Day 1, GI function will be assessed to determine return of GI function. Daily GI assessments will be collected until either the subject has had return of GI function or Hospital Discharge. If, while still in the hospital, GI function deteriorates to the point of no longer being able to tolerate an oral diet and pass stool, daily measurements should be collected again until the subject has had return of GI function.

Data for this assessment will include but not be limited to:

- Nausea and vomiting (either subject reported or recorded as presence or absence, date and time, including VRS [[Appendix 3](#)]),
- Passing of flatus (either subject reported or Investigator/delegated site personnel reported during a 24-hour calendar day; date and time of first flatus where only the first observance is recorded; in any instance where subject has post-operative complications and experiences ileus as decided by Investigator, the next flatus event should be recorded);
- Passing of stool from anus or ostomy (recorded as presence or absence and date and time);
- Presence of NG/OG tube (including date and time).
- Ability to tolerate liquid diet (liquid diet ordered, subject is able to sustain oral liquid intake without need for IV fluid administration, and total liquid volume over a 24-hour calendar day);
- Ability to tolerate a solid diet (solid diet ordered and date and time of solid food ingestion without significant nausea or vomiting for 4 hours).
- If a subject experiences a POI event during hospitalization, this event will be recorded, including date and time as an AE/SAE.

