6.14. Hospital Discharge

Subjects may not be discharged until all of the following criteria are met:

- Passage of stool
- Ability to tolerate solid food and drink comfortably
- Adequate oral analgesia
- Subject's willingness to be discharged.

Information related to Hospital Discharge after the first bowel resection will be recorded during the Post-Surgical period as:

- When discharge order is written (date and time)
- When subject departs from the hospital (date and time)

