7.15.2. Withdrawal from the Study

In the event that the subject, the subject's legal representative, the Investigator, or the Sponsor decides that the subject should be withdrawn from the study, all scheduled study assessments will be discontinued.

A subject may decide to withdraw from the study at any time. If a subject refuses to take study drug, the subject should be withdrawn from study participation. If the subject did take a portion of the study drug, the subject should remain in the study unless consent is withdrawn.

The Sponsor or its designees must be alerted if a subject is withdrawn from the study. A subject will be withdrawn from the study in the following situations:

- The subject or the subject's legal representative withdraws consent.
- The subject did not take any portion of study drug prior to surgery.
- The Investigator or the Sponsor, for any reason, stops the subject's participation in the study.

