9.3.2. Bowel Function

The primary efficacy analysis will be a time to event analysis (e.g., Cox proportional hazard model) with a main effect of treatment and stratified by surgery type (laparotomy versus minimally invasive approaches) and stoma (planned stoma versus no stoma). The p-values between the treatment groups will be evaluated using the Wald chi-square test. The magnitude of the treatment effect will be presented as the difference between the LB1148 and placebo arms in mean time to event (estimated by area under the Kaplan-Meier survival curve).

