4 GENERAL METHODS

4.1 Analysis Populations

Due to coronavirus disease 2019 (COVID-19), some subjects enrolled and randomized prior to 01Jan2022 were released from the hospital prior to achieving GI2. In addition, subjects were randomized based on whether the surgery was to include a stoma or not and a subject was considered completed at Study Day 30, e.g., the second surgery was optional. Protocol Amendment 5 and 6 require subjects to have a stoma during the first surgery and require the second surgery for the subjects to be considered complete. The primary endpoint is now comparing the change from baseline in extent and severity of intra-abdominal adhesions rather than GI2 among subjects treated with LB1148 or placebo. These circumstances and changes require corresponding updates to the populations defined in the Study Protocol.

The **modified Intent-to-Treat (mITT)** population includes all randomized subjects who received any investigational test article on or after 01Jan2022, where subjects will be analyzed according to the treatment to which they were randomized.

Safety Population: The safety population will be defined as all subjects who receive any amount of investigational test article. Subjects will be analyzed according to the treatment actually received.

The **Per Protocol Population (PP)** includes subjects in the mITT population who met all inclusion and no exclusion criteria, received the complete appropriate study dose, and had no important protocol deviations or violations, where subjects will be analyzed according to the treatment to which they were randomized.

Study subjects may be replaced if found to be ineligible (violation of one or more inclusion/exclusion criteria), or if following randomization, did not go on to receive ANY amount of investigational test article.

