Selected time-to-event secondary efficacy endpoints (See Table in Section 11.5) will be analyzed using a stratified Cox PH model with treatment as the main effect, stratified by surgery type (laparotomy versus minimally invasive). In addition to surgery type, a categorical age (<65 years, ≥ 65 years) will be included. Nominal p-values will be reported. Comparison of treatment groups and assessment of the significance of the parameter estimates for surgery type will be made using the Wald chi-square test.

In addition to the semi-parametric Cox PH model, non-parametric Kaplan-Meier survival curves will be produced for the two treatment groups and compared using a stratified log-rank test; results from this test will be considered nominal/hypothesis-generating in nature. The number of hours to each endpoint will be presented in summary tables with descriptive statistics for the mITT (all variables selected) and PP populations (POI, GI2, and GI3 variables only).

Those endpoints defined as yes/no variables will be analyzed using a chi-square test for homogeneity of proportions.

All findings will be presented in subject listings for the mITT population, including calculated time to event efficacy variables.

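### SAP 11.4 censors lost or withdrawn subjects at Study Day 14 instead of when last known event-free, so unobserved time counts as event-free for seven secondary and exploratory endpoints

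*SAP*

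**What the plan says.** The SAP 11.4 table has three rows: death without the event, loss or withdrawal without the event, and no event within 14 days of surgery. Each has the same outcome, "Censoring at Study Day 14". Row 2 applies where the event has not occurred "and the subject is lost to follow-up or withdrew informed consent"; the date of leaving plays no part.

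The footnote applies the table to seven endpoints: GI2, GI3, bowel movement, liquid diet, solid diet, discharge order written and actual discharge. The first five are secondary (SAP 11.2.2). The two discharge endpoints are exploratory in SAP 11.3, although length of stay is a secondary objective in SAP 3.2. By the SAP 11.5 table, all seven have Kaplan-Meier analyses and six have Cox models; liquid diet has none.

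On what is observed after a subject leaves, Protocol 7.15.2 states that on withdrawal "all scheduled study assessments will be discontinued". Protocol 6.13 adds: "Daily GI assessments will be collected until either the subject has had return of GI function or Hospital Discharge".

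SAP 4.4.1 rules out imputation except for a missing clock time on a known date. Neither document gives a reason for the Day 14 rule in row 2 or a sensitivity analysis around it.

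**The concern.** A censoring time should be the last time a subject was known to be event-free. Under row 2, a subject who withdraws at hour 20 stays in every risk set to Day 14 as if observed without the event.

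Unless that subject would truly have stayed event-free, the arm's Kaplan-Meier times lengthen and its event rate falls in the Cox and stratified log-rank analyses. The events here are favourable, so a loss on LB1148 makes the drug look worse and a loss on placebo makes it look better. Equal loss pulls a true hazard ratio toward 1. In a proof-of-concept study with nominal p-values the estimates carry the message, and with about 30 subjects a single leaver can move them.

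**Working it through.** **Inputs.** The plan gives no loss rate, event-time distribution or effect size for these endpoints, so there is no figure of its own to reproduce. From the documents: at least 30 randomized subjects (SAP 4.3) at 1:1, so 30/2 = 15 per arm; horizon 14 × 24 = 336 h; Cox model stratified by surgery type with an age category (SAP 11.2.2). Assumed: lognormal GI2 time, median 72 h, log-SD 0.6; surgery type split 50/50 (log-time effect 0.2); 40% aged 65 or over (effect 0.1); loss at 12-30 h, counted only if the subject is still event-free. A hazard ratio (HR) above 1 favours LB1148.

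**Excess time per leaver.** 336 − E[min(T, 336) | T > loss time] = 248.5 h. Spread over one arm, 248.5/15 = 16.6 h on the mean; the simulated shift was 16.1 h. This bears only on the mean-difference measure in Protocol 9.3.2 (area under the Kaplan-Meier curve), which the SAP does not repeat.

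**One or two early losses** (Monte Carlo, 2,000 to 6,000 runs per row). Each triple is SAP rule / last-contact censoring / no loss.

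| Scenario | HR | Rejection, % |
|---|---|---|
| No effect, one LB1148 loss | 0.82 / 1.00 / 1.00 | 5.5 / 5.4 / 5.5 |
| No effect, two LB1148 losses | 0.68 / 0.99 / 1.00 | 10.7 / 6.0 / 6.4 |
| Medians 54 vs 72 h, one LB1148 loss | 1.29 / 1.69 / 1.68 | 5.9 / 23.2 / 23.4 |
| Medians 54 vs 72 h, one placebo loss | 1.94 / 1.68 / 1.68 | 32.4 / 22.6 / 23.4 |

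In the first row the mean SE of log HR is 0.417, and |ln 0.82|/0.417 = 0.198/0.417 = 0.48, about half a standard error. The difference in Kaplan-Meier medians is +4.0 / −1.2 / +0.2 h. Repeat runs of the one-loss rows with separate code gave SAP-rule HRs of 0.81-0.83, 1.24-1.26 and 1.95-2.00, which agree within simulation error.

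**Equal random loss**, medians 54 vs 72 h (5,000 runs each). The chance of at least one leaver among 30 is 1 − (1 − r)^30.

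| Loss rate r | P(at least one) | HR, SAP / last contact / no loss |
|---|---|---|
| 1% | 0.26 | 1.64 / 1.67 / 1.67 |
| 2% | 0.455 | 1.61 / 1.67 / 1.67 |
| 1 in 15 | 0.874 | 1.51 / 1.68 / 1.67 |

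At 1 in 15, rejection is 16.8 / 21.4 / 22.1%. The area difference barely moves (−20.6 / −20.9 / −20.9 h), but its SD rises to 29.1 h, from 18.6 h with last-contact censoring and 17.8 h with no loss.

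**Sensitivity to the assumptions** (no effect, one LB1148 loss, SAP rule): HR 0.87 at median 36 h, 0.83 at median 120 h, 0.90 with loss at 48-72 h, 0.82 with no surgery or age effect.

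**Large-sample check.** This used 200,000 per arm, exponential times, placebo median 72 h, and loss uniform over 0-96 h. With no true effect, the SAP rule gives HR 1.17 when 5% on LB1148 and 15% on placebo are assigned a loss time, and 0.86 with the rates reversed. It gives 1.36 at 0% vs 20%, and 0.73 at 20% vs 0%. A true HR of 1.5 shrinks to 1.43, 1.39 and 1.34 at equal loss of 5, 10 and 20%. Censoring at loss recovers the truth throughout (0.995-1.002, or 1.494-1.506).

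**Informative loss.** If the leaver would truly have stayed event-free to Day 14, the SAP rule gives HR 0.81, which matches full follow-up (0.81), and last-contact censoring gives 1.00.

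**The case against.** The strongest objection is reach. Protocol 6.14 says "Subjects may not be discharged until all of the following criteria are met", and the criteria include passage of stool and tolerated solid food. A subject discharged under them has already had most of these events. Row 2 is left mainly with an inpatient who withdraws before the event, and there may be none. The early departures that the SAP does record, subjects "released from the hospital prior to achieving GI2" (SAP 4.1), predate 01Jan2022 and are outside the mITT population. All of this stands. It limits the impact but does not make the rule right.

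The early-loss figures are also conditional: they assume a loss occurs, and at a time when few subjects have had the event. That is fair, and the results for 1-2% loss and for later loss are the more sober guide.

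Row 2 might be defended as a worst case, in the spirit of SAP 4.4.1. But that rule covers only missing clock times, SAP 11.4 does not invoke it, and a longest-time rule is not conservative when the leaver is on placebo. Row 1 is defensible because a subject who has died can never have the event; that argument does not carry over to withdrawal.

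Protocol 6.13 is secondary support, since a discharged subject is not thereby lost; Protocol 7.15.2 carries the point. A subject discharged event-free who stays in the study would fall under row 3 with the same gap in observation, but the discharge criteria leave that group nearly empty.

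Finally, last-contact censoring assumes non-informative loss, which stalled recovery could break. That stands, and it is why both analyses should be reported.

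**Conclusion.** The concern holds. As written, row 2 treats unobserved time as event-free for seven endpoints, and nothing elsewhere in the documents corrects or justifies it. If an early loss occurs among about 15 per arm, the hazard ratio for that endpoint shifts by roughly half a standard error, in a direction that depends on the arm. At 1-2% equal loss the expected shift is only 0.03-0.06 from 1.67. These sizes rest on assumed event times, loss times and loss rates. With no pre-event loss the two rules give identical results. P-values are nominal and the primary adhesion endpoint is unaffected, so this should be fixed but does not threaten the main result.

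**What to change.** In SAP 11.4 row 2, censor lost or withdrawn subjects at the last time they were known to be event-free. That is the last GI assessment or, for the two discharge endpoints, the last time known to be in hospital. Keep Day 14 censoring for deaths and for subjects followed event-free to Day 14. Retain the present row 2 rule as a labelled sensitivity analysis, and report the number of row 2 subjects by arm for each endpoint.

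The cost is one table row, a small programming change and one extra output; no new data are needed. The downside is the non-informative-loss assumption, which the retained sensitivity analysis addresses.

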11.5 Efficacy Time-to-Event Parameter by Analysis Type

Number of hours to Analysis	Cox PH		Kaplan-Meier		Other	
	mITT	PP	mITT	PP	mITT	PP
GI2	Yes	Yes	Yes	Yes	Frequency Table	Frequency Table
Bowel movement within 14 days	Yes	No	Yes	No	Frequency Table	No
NG/OG use (insertion, reinsertion)	No	No	No	No	Frequency Table only	No
NG/OG removal	No	No	No	No	Listing only	No
Liquid oral diet	No	No	Yes	No	Frequency Table	No
Solid oral diet	Yes	No	Yes	No	Frequency Table	No
GI3	Yes	Yes	Yes	Yes	Frequency Table	Frequency Table
POI within 14 days	Yes	Yes	Yes	Yes	Frequency Table	Frequency Table

Number of hours to Analysis	Cox PH		Kaplan-Meier		Other	
POI after discharge	No	No	No	No	Included in Frequency Table for POI within 14 days	No
Discharge order written	Yes	Yes	Yes	Yes	No separate descriptive Frequency Table	No separate descriptive Frequency Table
Actual discharge	Yes	Yes	Yes	Yes	No separate descriptive Frequency Table	No separate descriptive Frequency Table
Standard discharge	No	No	No	No	Listing only	No
Nausea	No	No	No	No	Listing only	No
Vomiting	No	No	No	No	Listing only	No
Flatus	No	No	No	No	Listing only	No

12 SAFETY ANALYSIS

12.1 Adverse Events

All adverse events will be coded using the Medical Dictionary for Regulatory Activities (MedDRA) coding system (Version 25.0). Frequency tables will be presented by treatment group for all adverse events (AEs) by system organ class and preferred term for the safety population. Frequency tables will also be presented for AEs leading to discontinuation of test article, AEs by maximum severity (per CTCAE Version 5.0 Section 7.11 Study Protocol), AEs related to test article, and serious AEs. Subject listings of all AEs will also be provided for the safety population.

In all displays, adverse events will be displayed by MedDRA System Organ Class (SOC) and Preferred Terms. Subjects who have the same AE occur more than once will be counted only once for that event. Subjects who have more than one AE within a system organ class will be counted only once in that system organ class. (The addition of severity or relatedness follow the same pattern.)

In addition, frequency tables by treatment group for all AEs by system organ class and preferred term will be presented for the following populations:

- Patients who have had chemotherapy in the last 60 days
- Patients with a venous port or catheter
- Patients with varicose veins and superficial vein thrombosis
- Patients with varying degrees of obesity
 - Baseline BMI 30-35
 - Baseline BMI 35-40
- Patients who are smokers
- Patients with varying degrees of renal function

- Baseline eGFR 45-59
- Baseline eGFR 30-44
- Baseline eGFR 15-29
- Baseline eGFR < 15
- Patient age groups
 - 18-64 years
 - 65-80 years

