6.17. Appropriateness of Measurements

All procedures used to measure the safety and efficacy of LB1148 in this study are considered to be appropriate and necessary to obtain the required safety, tolerability, and efficacy data. The safety assessments used in this study, such as physical examination, vital signs, opioid use, laboratory assessments, and GI function assessments are widely used and are considered appropriate for monitoring subjects' health and well-being in this type of study. The measure used to evaluate pain levels is a validated and widely accepted rating scale used for clinical studies evaluating pain.

ADVERSE EVENTS ASSESSMENTS

AE data will be collected from first administration of study drug through Day 14, Hospital Discharge, or study termination, whichever comes first. Following discharge through the second surgery visit, any hospital readmissions will be recorded as SAEs.

AEs/SAEs related to the second surgery will also be collected.

Investigators are responsible for monitoring the safety of subjects who have entered this study and for alerting the Sponsor or its designees to any event that seems unusual, even if this event may be considered an unanticipated benefit to the subject.

The Investigator is responsible for the appropriate medical care of subjects during the study. The Investigator remains responsible for following, through an appropriate health care option, SAEs or AEs that caused the subject to discontinue before completing the study. The subject should be followed until the event is resolved or explained. Frequency of follow-up evaluation is left to the discretion of the Investigator.

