2 STUDY OVERVIEW

This is a multicenter, randomized, double-blind, parallel, placebo-controlled, proof-of-concept, adaptive design, Phase 2 study to evaluate LB1148 for return of GI function, reduction of POI and intra-abdominal adhesions in subjects undergoing elective bowel resection with a planned stoma. The study is randomized to control for factors known and unknown between the treatment groups, and neither the Investigator nor the subject will know which treatment the subject will receive in order to avoid any bias in the study assessments.

This study is composed of 5 periods: Screening, Surgical, Post-Surgical, Follow-Up, and Second Surgery.

Subjects scheduled for elective bowel resection, aged 18 to 80 years inclusive, will be screened within 42 days of randomization (Study Day 1). Subjects who meet all inclusion and no exclusion criteria, and provide written informed consent, will be stratified by: 1) surgical approach (either minimally invasive technique or laparotomy) and 2) with or without a planned stoma, and then randomized to receive a split oral liquid dose of LB1148 or placebo (polyethylene glycol [PEG], glucose, and electrolytes) in a 1:1 ratio. (Note: Stratification factor #2 does not apply for subjects randomized after 01Jan2022 based on Protocol Amendment #5 updates because all subjects should have a stoma.)

All subjects will receive 350 mL of study drug (test article) 6-10 and 2-6 hours prior to surgery (Study Day 1/2). Subjects will then undergo the first surgery. Prior to surgical closure, the investigator will determine the incidence, extent, and severity of adhesions using the Intra-Abdominal Adhesion Extent and Severity Assessment Worksheet (Study Protocol, Appendix 5).

Subjects will be assessed for safety and tolerability, including AEs, physical exam, vital signs, clinical lab tests (chemistry, coagulation, and hematology) while in the hospital and on Day 30. Subjects will be monitored for return of bowel function while in the hospital and discharged following tolerance of solid food and first bowel movement.

Within 8 months of enrollment, subjects will undergo a second surgery for the purpose of ostomy takedown or other planned abdominal surgery, at which time the surgeon will determine the incidence, extent, and severity of adhesions. If a subject is not ready for the second surgery by 8 months, the investigator may consult with Medical Monitor to obtain window approval.

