5 SUBJECT DISPOSITION

The number of subjects who are treated, complete the study, and reasons for discontinuation from the study will be summarized in tabular format for the safety population separately by subjects enrolled prior to 01Jan2022 and subjects enrolled after 01Jan2022. Subject disposition will also be displayed for the safety population in a subject listing.

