14 INTERIM ANALYSES

An interim analysis of limited efficacy, safety, and tolerability was proposed in the initial study protocol. The purpose of the interim analysis was to allow for sample size adjustment based on observed data, e.g., an increase in sample size, if needed. An interim analysis with primary endpoints return of bowel function (GI2) and LOS (Discharge Order Written) was performed in the spring of 2020. Efficacy and safety tables were provided to the sponsor in May of 2020.

The change in primary endpoint with Protocol Amendment #5 modified the emphasis of this study. No change in sample size was made because the endpoints reviewed were no longer the primary endpoints. As previously discussed in Section 4.1, the subjects used for this analysis are now included only in the safety population.

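### SAP 12.1 pools serious AEs, and the late part of the other AE tables, over two enrolment eras with different follow-up, so the crude SAE percentage matches neither follow-up period

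*SAP*

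**What the plan says.** On the safety tables, SAP 12.1 states: "Frequency tables will be presented by treatment group for all adverse events (AEs) by system organ class and preferred term for the safety population". It adds tables for AEs leading to discontinuation of test article, maximum severity, related AEs and serious AEs. The listed subgroups are chemotherapy, venous port or catheter, varicose veins, obesity, smoking, renal function and age. Enrolment era is not among them.

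SAP 4.1 sets no date limit on the population: "The safety population will be defined as all subjects who receive any amount of investigational test article". SAP 14 says of the interim-analysis subjects that "the subjects used for this analysis are now included only in the safety population".

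On follow-up, SAP 4.1 says that before 01Jan2022 "a subject was considered completed at Study Day 30, e.g., the second surgery was optional". Amendments 5 and 6, by contrast, "require subjects to have a stoma during the first surgery and require the second surgery for the subjects to be considered complete". SAP 2 plans that surgery within 8 months of enrolment and allows more time: "If a subject is not ready for the second surgery by 8 months, the investigator may consult with Medical Monitor to obtain window approval".

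The opening text of Protocol Section 7 ends general AE collection at Day 14, discharge or study termination, whichever is first. It then continues: "Following discharge through the second surgery visit, any hospital readmissions will be recorded as SAEs". AEs and SAEs related to the second surgery are also collected. Protocol 7.9 ends the readmission window at the Month 3 visit, and 7.13 also refers to Month 3.

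The SAP uses an era split elsewhere. Section 5 summarizes disposition "separately by subjects enrolled prior to 01Jan2022 and subjects enrolled after 01Jan2022", and Section 8 divides the surgery table at the same date.

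**The concern.** A crude percentage of subjects with an SAE can be read only against a known period of observation. Here one column would combine subjects whose participation ended at Day 30 with subjects who could contribute readmissions and second-surgery events for months longer. The result is an average over two follow-up lengths, weighted by how many subjects each era happened to enrol.

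Readers take absolute SAE rates from this table, and the study is meant to inform later trials. The rate most relevant to the design now in force, with a stoma and a required second surgery, would be pulled towards the lower 30-day figure. The SAP treats the eras as different for efficacy, disposition and surgery, and gives no reason for treating them as one in the AE tables.

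**Working it through.** The plan states no SAE rate and no safety sample size, so there is no figure to reproduce. The check has two parts: a comparison of collection windows, and an illustration on stated assumptions.

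**1. Collection windows**

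| Event type | Enrolled before 01Jan2022 | Enrolled on or after 01Jan2022 |
|---|---|---|
| General (in-hospital) AEs | Protocol text then in force not available | First dose to Day 14, discharge or termination, whichever is first |
| Readmissions recorded as SAEs | To Day 30, inferred from completion at Day 30 | To the second surgery (Protocol 7) or Month 3 (7.9, 7.13) |
| Events related to the second surgery | Only if the optional surgery took place | Collected at the required surgery |

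The mismatch lies in the last two rows. It therefore falls on the serious-AE table and on the readmission and second-surgery part of the all-AE, severity and relatedness tables. If in-hospital AEs had the same window in both eras, pooling mixes only the populations, for example subjects with and without a stoma.

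**2. Inputs for the illustration**

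- Earlier-era size n1: 50-60, from the planned interim size in SAP 4.3, and 100 as an assumed upper value.
- Later-era size n2: 30-40, from SAP 4.3. The text does not say whether the 40 are additional subjects; I assume that they are.
- Follow-up: 30 days in the earlier era. In the later era, 120-243 days (about 4 to 8 months), assumed within the 8-month limit, or 90 days under the Month 3 wording.
- SAE rates: assumed, because the documents give none.

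**3. Weight of the later era**

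Share of subjects = n2/(n1 + n2): lowest 30/130 = 23%, highest 40/90 = 44%.

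Share of readmission person-time = n2·f/(30·n1 + n2·f):

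- Second-surgery window, lowest: 30·120/(3000 + 3600) = 55%.
- Second-surgery window, highest: 40·243/(1500 + 9720) = 87%.
- Month 3 window: 2700/(3000 + 2700) = 47% to 3600/(1500 + 3600) = 71%.

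**4. Pooled percentage** = (n1·p1 + n2·p2)/(n1 + n2)

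- p1 = 10%, p2 = 35%: (10 + 10.5)/130 = 15.8% to (5 + 14)/90 = 21.1%.
- p1 = 15%, p2 = 40%, with n1 = 50-60: (9 + 12)/90 = 23.3% to (7.5 + 16)/90 = 26.1%.
- p1 = 10%, p2 = 20%, with n1 = 50-60: (6 + 6)/90 = 13.3% to (5 + 8)/90 = 14.4%.

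In each case the pooled figure lies between the two eras' rates and equals neither. If both eras had the same window and the same rate, pooling would change nothing.

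**5. Comparison between arms, with no drug effect**

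With exact 1:1 allocation within each era, the difference is 0. Suppose the earlier era splits 30:30 and the later era 20:15, at rates of 10% and 35%. Then (3 + 7)/50 = 20.0% against (3 + 5.25)/45 = 18.3%, a difference of 1.7 points. Its standard error is √(0.200·0.800/50 + 0.183·0.817/45) ≈ 8.1 points, so the shift is about 0.2 standard errors.

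**The case against.** The strongest case against is that little of the safety output is affected, and what is affected can be recovered. Four stronger conclusions that a reader might draw are not supported.

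- *That every table in SAP 12.1 mixes follow-up periods.* General AEs stop at Day 14 or discharge under the current protocol, and discontinuation of test article concerns dosing completed before surgery. Long follow-up adds mainly readmissions and second-surgery events.
- *That the planned readmission rate is diluted.* Readmission is a separate endpoint in SAP 11.3, summarized in the mITT population (dosed on or after 01Jan2022), and its objective in SAP 3.3 is limited to 30 days after the first surgery.
- *That a split at 01Jan2022 separates the old and new eligibility rules.* Amendment 6, which removed the exclusions for thromboembolic risk factors and BMI above 40 among others, is dated 26 August 2022. Both sets of exclusions can therefore occur within the later era.
- *That the arm comparison is materially biased.* Randomization is 1:1, SAP 12.1 plans no between-arm test, and an assumed imbalance moved the difference by only about 0.2 standard errors.

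The contrast in follow-up is also not perfectly clean. Some earlier subjects may have had the optional surgery, and the amendment summary shows that SAE reporting was extended to Month 3 in June 2021. All AEs will be listed with a study day, so the split could be rebuilt by hand.

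These points narrow the concern but do not remove it. The serious-AE table still combines unequal windows, and a listing does not replace a prespecified table.

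**Conclusion.** The concern holds for the serious-AE table and for the readmission and second-surgery events within the all-AE, severity and relatedness tables. Followed as written, SAP 12.1 yields a crude SAE percentage over unequal follow-up that represents neither the 30-day period nor the period to the second surgery. The harm is to absolute rates.

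Its size cannot be known from the documents. On assumed rates of 10% and 35%, the pooled 16-21% is about 45-60% of the rate to the second surgery. That illustration also assumes the era sizes above, no optional second surgeries among earlier subjects, and follow-up of all later subjects to the second surgery. A narrower gap between eras, or the Month 3 window, would make the distortion smaller.

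**What to change.** In SAP 12.1:

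- Add columns by treatment for subjects enrolled before, and on or after, 01Jan2022 beside the pooled total, following Sections 5 and 8.
- In the serious-AE table, separate events through Day 30 from later readmissions and second-surgery events.
- Report the later events with the later-era N as denominator. List separately any that come from earlier subjects who had the optional surgery.
- Describe the columns as a split by enrolment era, not by Amendment 6 eligibility.

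In the Protocol, reconcile the SAE reporting window in the opening text of Section 7 with 7.9 and 7.13, so that the later-event rows refer to one stated period.

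No new data and no additional inference are needed. The cost is SAP wording, extra table columns and smaller denominators in each column.
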